At this visit, participant's height and weight will be measured. ~30 mL of blood will be collected into heparinised tubes to provide whole blood and plasma. After blood collection, participants will be given breakfast (orange juice, toast and jam, tea or coffee) and their habitual diet will be assessed using a Food Frequency Questionnaire. They will complete a gastrointestinal tolerance questionnaire and the Bristol stool chart. During the visit they will provide a urine sample if possible; otherwise they will take a urine collection kit away with them to collect their sample at home. Participants will be provided with a kit to collect a faecal sample to be done prior to using any study products (e.g. later that same day as the clinic visit or the next day) and instructions on how to collect and store the sample. Participants will complete a log recording collection of the sample. A courier service will be used to collect faecal samples from participant's homes.

Participants will then be randomised to one of two groups (corn fibre (20 g/day) or placebo (maltodextrin (calorie-matched dose)) and will receive 4 months supply along with a diary to record that they have taken their supplement each day. The supply of study products will last the 12 week intervention with some to spare in case of a delay in returning for V2. The study materials will be provided in sachets to be stirred into cold water or fruit juice and drunk with meals twice per day. Both corn fibre and maltodextrin are tasteless. Blinding, randomisation, and supplement packaging will be completed by individuals independent of the researchers involved in the study. Participants will be randomised stratified by sex to ensure equal numbers of males and females in each treatment group.

Between visits 1 and 2

Participants will consume soluble corn fibre or maltodextrin daily. They will record this in a daily diary.

Participants will be contacted by the researcher at week 4 and week 8 and will be requested to bring unused supplements to their end of study clinic visit (visit 2; week 12). These will be used to assess compliance.

Visit 2

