Ingredient manufactured by Tate & Lyle

Participant Randomisation Number/Code

Investigator name

For clinical trial use only

Batch/Lot number

Storage conditions / keep away from children (if applicable)

Product is packaged in an area with other allergens

Directions for use

Emergency Contact Number

Expiry date

Packaging and labelling will be performed by Calleva Ltd. Labelling of individual boxes with participant randomisation number will be performed by an independent to the study personnel at University of Southampton (keeping study personnel blinded).

Each box will contain 225 sachets allowing for 2 sachets per day, for 84 days (12 weeks) and an extra 57-day supply, in case of delay of visit or loss of investigational product.

9. Compliance

Participants will keep a daily diary recording the use of sachets. They will be asked to return all used and unused sachets at visit 2. The diary and the returned unused sachet count will be used to estimate compliance.

Compliance will be calculated as follows:

$$Compliance \,\% = \, \frac{\textit{Number of sachets dispensed} - \textit{number of sachets returned}}{\textit{number of days in intervention period x 2 doses per day}}$$

In the statistical analysis, overall compliance will be considered.

If a participant states that they have not returned all unused sachets (e.g. forgot to return, loss), these details will be recorded. Participants must have consumed between 80 and 120 % of the investigational product, in order to be deemed compliant. Non-compliant participants will be withdrawn from the per-protocol analysis.

10. Variables and analyses

Markers of immunity and inflammation will be measured in blood samples collected at visits 1 and 2. There is no single marker of "immunity" and therefore a range of static and dynamic markers of innate and acquired immune responses should be measured, as recommended by Albers et al. [32]. Neutrophil phagocytosis of E. coli (median fluorescence intensity reflecting the number of bacteria taken up per neutrophil) will be the primary outcome. All other markers are secondary outcomes.

The following will be measured:

- Immune cell phenotypes in blood (T cells, B cells, monocytes, T helper cells, cytotoxic T cells, regulatory T cells, natural killer cells): flow cytometry [real-time measurement]
- A panel of cytokines and chemokines in plasma: multiplex immunoassay [measurement in stored samples]

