11. Sample size and statistical analysis

Neutrophil phagocytosis of E. coli will be the primary outcome. Wenisch et al. [33] reported that the number of E. coli taken up by neutrophils was lower by 25% in people aged 62 to 83 years compared to those aged 38 to 56 years. This difference is considered to be relevant to age-related susceptibility to bacterial infection. Some studies of probiotics and prebiotics have reported

enhanced phagocytosis including in older people. The sample size of the current study is based on a 20% increase in neutrophil phagocytosis of E. coli, an effect size based upon the prior studies of probiotics and prebiotics. Using in-house data on mean and SD phagocytosis (median fluorescence intensity using a flow cytometry based commercial kit) 27 participants per group are required to give 80% power to detect a 20% increase as significant with a type-1 error of 5%. To account for 25% drop-out 36 participants will be recruited into each group (i.e. 72 participants in total). All other measurements are secondary outcomes.

12. Data handling and statistical analysis

Data will be entered onto password protected Excel files. Changes between visits 1 and 2 for all outcomes will be compared between groups using unpaired tests. The exact tests used will depend upon the distribution of the data. Where data are not normally distributed, they will be log transformed to attempt to achieve a normal distribution. Regression analyses considering variables such as age, sex and BMI will also be conducted. Statistical analysis will be conducted using the current version of SPSS.

13. Study setting

Clinic visits will take place in the NIHR Clinical Research Facility at Southampton General Hospital. This is an MHRA compliant research facility.

Sample processing and storage and laboratory analysis will take place in laboratories within the Faculty of Medicine, University of Southampton [apart from analysis of faecal bacteria which will be conducted at Catholic University of Louvain, Brussels].

All activities will be according to GCP and follow GDPR protocols.

All staff will be fully trained, including in GCP, with training records.

All laboratory processes will follow SOPs.

14. Adverse events

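### The main test compares unadjusted changes; ANCOVA on the baseline value and sex would be more precise at no cost, and section 11 should say which SD its 80% power rests on

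*Protocol*

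**What the plan says.** Protocol section 10 names the primary outcome: "Neutrophil phagocytosis of E. coli (median fluorescence intensity reflecting the number of bacteria taken up per neutrophil) will be the primary outcome". It is measured at visits 1 and 2, so every participant who attends both has a baseline value.

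Section 12 gives the comparison: "Changes between visits 1 and 2 for all outcomes will be compared between groups using unpaired tests". The exact test depends on the distribution, and non-normal data are to be log-transformed. The section then adds: "Regression analyses considering variables such as age, sex and BMI will also be conducted". The word *also* places these regressions beside the main test, and the baseline value of the outcome is not among the variables named.

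Section 5 (Visit 1) says: "Participants will be randomised stratified by sex to ensure equal numbers of males and females in each treatment group".

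Section 11 sizes the trial. "The sample size of the current study is based on a 20% increase in neutrophil phagocytosis of E. coli", and "Using in-house data on mean and SD phagocytosis (median fluorescence intensity using a flow cytometry based commercial kit) 27 participants per group are required" for 80% power at a 5% type-1 error. Allowing for 25% drop-out gives 36 per group, 72 in total. The section shows no mean, no SD and no correlation between visits, and it does not say whether the SD is of single values or of changes.

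**The concern.** Two things do not fit together well.

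First, a change score subtracts the whole baseline value, as if the slope of visit 2 on visit 1 were 1. With equal variances at the two visits that slope is the correlation rho, which is below 1 for any real assay. Subtracting the full baseline therefore adds noise that ANCOVA avoids by estimating the slope. Sex, the stratification factor, is also left out of the main test.

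Second, section 11 speaks of the mean and SD of phagocytosis, while the test in section 12 is on its change. These two SDs are equal only at one value of rho. If the sample size used the first and the analysis uses the second, the stated 80% may not describe the planned test.

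At stake is the precision of a primary result resting on about 54 completers (2 x 27), and whether the power figure belongs to the analysis that will be run.

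**Working it through.** **Inputs from the protocol (section 11):** 27 completers per group, 80% power, 5% type-1 error, 20% increase, 25% drop-out.

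**Assumptions, because the protocol does not give them:** two-sided test; equal SD at the two visits; rho between 0.2 and 0.7.

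**Step 1: the plan's own figures.** Drop-out: 27 / (1 − 0.25) = 36 per group, 72 in total, as stated. The 27 cannot be derived forwards because the mean and SD are not shown. Solving backwards with the noncentral t, 27 per group at 80% power requires a standardised difference d = 0.777. A 20% effect then implies a CV of 0.20 / 0.777 = 25.7%.

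**Step 2: SD of each analysis, relative to a single-visit SD.**
- Change score: SD × √(2(1 − rho))
- ANCOVA on baseline: SD × √(1 − rho²)
- Variance ratio, ANCOVA to change: (1 − rho²) / (2(1 − rho)) = (1 + rho)/2. At rho 0.5 this is 0.75, so 25% less variance.

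**Step 3: if the in-house SD is of single-visit values.** Divide 0.777 by each factor and compute power with 27 per group:

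| rho | change factor | power, change | ANCOVA factor | power, ANCOVA |
|---|---|---|---|---|
| 0.2 | 1.265 | 60% | 0.980 | 82% |
| 0.3 | 1.183 | 66% | 0.954 | 84% |
| 0.4 | 1.095 | 72% | 0.917 | 86% |
| 0.5 | 1.000 | 80% | 0.866 | 90% |
| 0.7 | 0.775 | 95% | 0.714 | 98% |

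The change-score test reaches 80% when 2(1 − rho) = 1, that is at rho = 0.5. If all 36 per group complete, the condition is approximately 2(1 − rho) = 36/27 = 1.333, so rho is about 0.33. For 80% power at rho 0.3, the change score needs 38 completers per group and ANCOVA 25.

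**Step 4: if the in-house SD is already of changes.** The change-score test has the stated 80% at any rho. ANCOVA has d = 0.777 / √((1 + rho)/2):
- rho 0.3: d = 0.964, power about 93%
- rho 0.5: d = 0.897, power about 90%
- rho 0.7: d = 0.843, power about 86%

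The further gain from adjusting for sex cannot be computed from the document.

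**The case against.** The strongest reply is that nothing planned is invalid. Under randomisation, an unpaired test on change is unbiased for the treatment effect and controls type-1 error. This stands. A chance baseline imbalance can distort a particular result, but that is bias conditional on the imbalance, not bias of the planned test.

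A reader might infer from the table that the trial is underpowered. The document does not support this. It gives no rho, and nothing in it shows that rho is below 0.5. The single-visit reading of the SD is the natural one but is unconfirmed, and on the other reading there is no shortfall. The 0.5 threshold also applies only if the full 25% drop-out occurs.

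The regressions do name sex, and the wording *such as* does not exclude the baseline value. So the plan as a whole does not ignore the stratification factor; the main test does.

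The power figures assume equal variances and an analysis on the scale used for sizing. If the data are log-transformed, the algebra is the same, but the SD and correlation are those of the logged values, and a 20% increase becomes ln(1.2) = 0.182.

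The last reply is that model choice belongs in a statistical analysis plan, which may exist. For finer detail that is fair. Here, though, the protocol itself selects the comparison for all outcomes, so its choice is open to comment.

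**Conclusion.** The point holds as one of efficiency and clarity. The planned test is valid, but a more precise one is available from data already collected. With equal visit variances, ANCOVA has (1 + rho)/2 of the change-score variance, which is smaller for every rho below 1. This does not depend on which SD was used in section 11.

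Whether the stated 80% applies to the planned test cannot be settled from the protocol. With a single-visit SD it does so only for rho of at least 0.5 at 27 completers per group, or about 0.33 at 36. With an SD of changes it does so at any rho. Under either reading, for rho of 0 or more, ANCOVA with 27 per group keeps essentially 80% power or better.

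A proven loss of power is not established, and neither is a flaw that must be corrected before the trial can be interpreted. This is a recommended free improvement.

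**What to change.** In section 12, name one primary analysis: ANCOVA of visit 2 neutrophil MFI (log-transformed if needed) on treatment group, with visit 1 MFI on the same scale and sex as covariates, reporting the adjusted difference with its 95% CI. Use the same model for the continuous secondary outcomes. Keep the unadjusted comparison of changes and the models with age and BMI as supportive analyses.

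In section 11, state whether the in-house SD is of single-visit values or of changes, give its value with the mean, and tie the 80% power to the ANCOVA.

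The cost is a wording change in two sections, made before unblinding. It needs no extra participants, visits or measurements, and SPSS, the package named in section 12, fits the model.

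### The scale and test for the primary outcome are left to the observed distribution, and the unadjusted test of changes gives up power that a pre-named baseline-adjusted log model would recover

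*Protocol*

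**What the plan says.** The primary outcome is fixed in section 10 of the protocol: "Neutrophil phagocytosis of E. coli (median fluorescence intensity reflecting the number of bacteria taken up per neutrophil) will be the primary outcome". Section 12 then gives the analysis rule:

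- The quantity compared: "Changes between visits 1 and 2 for all outcomes will be compared between groups using unpaired tests".
- The choice of test: "The exact tests used will depend upon the distribution of the data".
- The transformation: "Where data are not normally distributed, they will be log transformed to attempt to achieve a normal distribution".
- A further analysis: "Regression analyses considering variables such as age, sex and BMI will also be conducted".

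The first rule applies to all outcomes, so the primary outcome is included. No normality criterion, default test or fallback is named. The regression is additional. It is not tied to the primary outcome, and the visit 1 value is not among the covariates listed.

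Section 11 plans on a relative effect ("The sample size of the current study is based on a 20% increase in neutrophil phagocytosis of E. coli") and states that "27 participants per group are required to give 80% power to detect a 20% increase as significant with a type-1 error of 5" per cent. The mean and SD come from in-house data and are not printed. Section 5 (Visit 1) stratifies randomisation by sex.

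**The concern.** Two things are left open that should be settled before any data are seen.

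The first is the effect measure. A t-test on raw changes estimates a difference in mean fluorescence units. A t-test on log(visit 2) minus log(visit 1) estimates a ratio. A rank test on changes estimates neither. Under section 12, which of these becomes the primary result depends on how the data look. The word used for what is logged is simply data. The only analysed quantity named is the change, which may be zero or negative and then has no logarithm, while the visit values are positive and can always be logged. A reader cannot tell which is meant.

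The second is efficiency. An unpaired test of changes ignores the fact that a high visit 1 value tends to be followed by a smaller rise. Adjusting for the visit 1 value uses data already collected and gives a more precise treatment comparison unless the visit correlation is close to 1. With 27 evaluable participants per group, that precision matters.

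**Working it through.** **Inputs from the protocol.** 27 evaluable per group, 80% power, 5% type I error, 20% increase, 25% drop-out (section 11).

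**Assumptions, because the protocol gives no figure.** Two-sided test; no mean change on placebo; the in-house SD is that of a single visit value; lognormal MFI; correlation between visits of 0.3, 0.5 or 0.7.

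**The plan's own figure.** The drop-out step reproduces: 27 / (1 − 0.25) = 36 per group, 72 in total. The 27 cannot be checked directly without the mean and SD, but it can be solved backwards:

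- standardised effect d = √2 × (1.960 + 0.842) / √27 = 0.762
- implied SD/mean = 0.20 / 0.762 = 26.2% (25.7% with the t distribution; about 29% if the test were one-sided)

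Nothing else in the protocol contradicts a CV of about 26%.

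**On the log scale.** SD of log MFI: s = √ln(1 + 0.262²) = 0.258. Target effect: ln(1.20) = 0.182.

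- SD of the log change: s√(2(1 − ρ))
- Residual SD after adjusting for log visit 1: s√(1 − ρ²)
- Ratio of the two variances: (1 − ρ²) / (2(1 − ρ)) = (1 + ρ)/2
- Approximate power: Φ(0.182/SD × √(27/2) − 1.960)

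For ρ = 0.5 the change has SD 0.258, so Φ(0.707 × 3.674 − 1.960) = Φ(0.64) = 74%. The adjusted model has SD 0.223, so Φ(0.816 × 3.674 − 1.960) = Φ(1.04) = 85%.

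| ρ | SD, log change | SD, adjusted | Variance ratio | Power by formula: change / adjusted | Simulated power: unpaired t-test of raw changes / adjusted log model |
|---|---|---|---|---|---|
| 0.3 | 0.305 | 0.246 | 0.65 | 59% / 78% | 61% / 77% |
| 0.5 | 0.258 | 0.223 | 0.75 | 74% / 85% | 74% / 83% |
| 0.7 | 0.200 | 0.184 | 0.85 | 92% / 95% | 91% / 94% |

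Formula and simulation agree to within about two percentage points. The gain comes from the baseline adjustment, not from the log. A log-ratio t-test without adjustment had simulated power of 60% and 73% at ρ = 0.3 and 0.5, about the same as the raw change. What the log contributes is a defined ratio that matches the planning effect.

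**Does the data-driven choice itself do harm?** One workable version of the rule was simulated: t-test on changes; if Shapiro-Wilk rejects normality, log-ratio t-test; if that is still non-normal, Mann-Whitney. At CV 26% the first check rejected normality in about one trial in five. Across this rule and a simpler choice between t-test and Mann-Whitney, at CVs of 26% and 60%, type I error lay between 4.6% and 5.5%. At CV 26%, power was 61% and 74% at ρ = 0.3 and 0.5, the same as for the plain t-test of changes.

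**The case against.** A reader might infer that the log step must break down, because changes are the only analysed quantity named and about half of the placebo changes would be zero or negative if placebo has no mean effect. The protocol does not support that. It says data, which can equally mean the recorded visit values, and log(visit 2) minus log(visit 1) exists for every positive pair. Nor does it say that undefined values would be dropped, so no selective loss of participants can be read into it. The sentence is ambiguous; it is not a stated error.

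A reader might also infer that the choice of test inflates the false-positive rate. That would need the test to be picked by its p-value. The protocol ties the choice to the distribution, and the simulation above shows that such a rule stays near 5%. The extra regression is not offered as a rival primary test either.

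It can further be said that a normality criterion, the order of transformation and a fallback test are matters for an analysis plan, which may exist unseen, and that a 20% difference in means can be planned coherently on the raw scale. Both points are fair. A raw-scale analysis would not be wrong, and a normality criterion missing from a protocol is no finding. What stands is that section 12 is not silent. It says that the observed distribution decides the test, with no exception for the primary outcome, and it fixes an unadjusted comparison of changes. An analysis plan that named one adjusted model would have to depart from that text.

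**Conclusion.** The point holds as one of specification and efficiency. The primary effect measure (difference or ratio) is not settled in advance, and the object of the log transformation is unclear. Type I error is not materially affected. Relative to the unpaired test of changes, a baseline-adjusted log model named now would raise power by about 16, 9 and 3 percentage points at visit correlations of 0.3, 0.5 and 0.7 (77 − 61, 83 − 74, 94 − 91). The gain shrinks as the correlation rises.

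These sizes rest on the assumptions listed above, mainly that the implied CV of 26% describes a single visit. If the in-house SD is instead that of the change, the planned power already refers to the change and the levels in the table move. The variance ratio (1 + ρ)/2 does not, so the adjusted model remains the more precise one. The planned sample size is unaffected. This is a worthwhile, nearly free improvement to the primary analysis, not a flaw that invalidates the trial.

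**What to change.** In section 12:

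1. State that any log transformation is applied to the visit 1 and visit 2 values before a change or model is computed.
2. Name one primary analysis: a linear model of log(MFI at visit 2) on treatment, log(MFI at visit 1) and sex (the stratification factor), reported as a geometric mean ratio with its 95% confidence interval. The planned effect then corresponds to a ratio of 1.20.
3. Make the raw-scale comparison of changes and rank-based tests sensitivity analyses, whatever the normality check shows.
4. Apply the same log-before-change rule to positive, skewed secondary markers such as plasma cytokines, CRP, faecal calprotectin and short chain fatty acids.

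The cost is a few sentences. No further data, visits or participants are needed.

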14.1 What is an adverse event?

An adverse event (AE) is defined as any untoward medical occurrence in a patient or clinical study subject administered an investigational product and which does not necessarily have a causal relationship with this treatment. An AE can therefore be any unfavourable and unintended sign (including an abnormal laboratory finding), symptom, or disease temporally associated with the use of an investigational product, whether or not related to the investigational product.

An adverse reaction is defined as all untoward and unintended responses to an investigational product related to any dose administered, i.e. where a causal relationship between the investigational product and an adverse event is at least a reasonable possibility.

An unexpected adverse reaction is an adverse reaction, the nature or severity of which is not consistent with the information about the investigational product or intervention in question set out in the Summary of Product Characteristics (see section 7).

An adverse event, adverse reaction, or unexpected adverse reaction, is defined as serious if it:

- a) results in death;
- b) is life-threatening;

Life threatening in the definition of a serious adverse event (SAE)/serious adverse reaction (SAR) refers to an event in which the subject was at risk of death at the time of the event; it does not refer to an event that hypothetically might have caused death if it were more severe.

c) requires hospitalisation or prolongation of existing hospitalisation;

In general, hospitalisation signifies that the subject has been detained (usually involving an overnight stay) at the hospital or emergency ward for observation and/or treatment which would not have been appropriate at the investigator site. When in doubt as to whether hospitalisation occurred or was necessary, the adverse event should be considered as serious. Hospitalisation for elective surgery or routine clinical procedures, which are not the result of an AE, need not be considered AE and should be recorded on a Clinical Assessment form and added to the study file. If something untoward is reported during the procedure, this must be reported as an AE and either 'serious' or 'non-serious' attributed according to the usual criteria.

- d) results in persistent or significant disability or incapacity;
- e) consists of a congenital anomaly or birth defect.

Medical judgement should be exercised in deciding whether an SAE/SAR is serious in other situations. Important SAE/SARs that are not immediately life-threatening or do not result in death or prolonged hospitalisation but may jeopardise the subject or may require intervention to prevent one or the other outcomes listed in the definition above, should also be considered serious.

A suspected serious adverse reaction (SSAR), is any serious adverse reaction that is suspected (possibly or probably) to be related to the investigational product.

A suspected unexpected serious adverse reaction (SUSAR) is an SSAR which is also "unexpected", meaning that its nature and severity are not consistent with the information about the investigational product in question set out in the IB.

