Participants will consume 20 g of soluble corn fibre or calorie-matched maltodextrin daily for 3 months. These materials will be supplied by Tate & Lyle as identical sachets to be stirred into cold water or fruit juice and drunk with meals two times per day. Tate & Lyle will be responsible for preparation, labelling and transportation of materials to the site. Study materials will be stored in a locked, limited access room on Level D of the IDS Building (University of Southampton, Southampton General Hospital campus) dedicated to this purpose. The soluble corn fibre will be PROMITOR® Soluble Fibre as used in the food industry. PROMITOR® Soluble Fibre has been shown to be well-tolerated even at high intake levels (40 g/day bolus or to a total of 65 g/day in multiple doses) [30]. The comparator will be MALTOSWEET™ G 120 (Maltodextrin Non-GMO) given at 2 g/day to match the calorie intake of the soluble corn fibre.

7. Summary of product characteristics

Investigational product

- Product name: PROMITOR® Soluble Fibre
- Active compound: 85A powder (PCR-negative)
- Manufactured by: Tate & Lyle
- Sachets packaged by Calleva Ltd
- Sachet: 12 g compound per Sachet (10 g fibre), consumed twice per day.

PROMITOR® Soluble Corn Fibre 85A is a glucose polymer obtained from partially hydrolysed corn starch and contains a mixture of α 1-6, α 1-4, and α 1-2 glucosidic linkages. In appearance it is an agglomerated powder, white and soluble in water.

It complies with US FDA Regulation 21CFR184.1444 - generally recognised as safe.

A sudden increase in dietary fibre may cause mild gastrointestinal disturbances, but these are generally transient and improve with adaptation to the dietary fibre source. PROMITOR® Soluble Fibre has been shown to be well-tolerated even at high intake levels (40 g/day bolus or to a total of 65 g/day in multiple doses) (30).

Placebo product

- Active compound: MALTOSWEET™ G 120 (Maltodextrin Non-GMO)
- Manufactured by: Tate & Lyle
- Sachets produced by Calleva Ltd
- Sachets: 2 g compound per sachet (0 g fibre), composed of: Maltodextrin

The placebo will be an isocaloric match using Maltodextrin (MALTOSWEET™ G 120). It is a white, practically odourless powder which is soluble in water.

MALTOSWEET™ G 120 complies with the requirements of EU Directives and Regulations in force on foods and food ingredients.

8. Labelling and packaging

The label will contain the following information:

University of Southampton Study code – xxxxx

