14.3 Causality

The relationship between the investigational product/procedure and the occurrence of each AE will be assessed and categorised as below by the chief investigator. The chief investigator will use clinical judgement to determine the relationship. Alternative causes, such as natural history of the underlying diseases, concomitant therapy, other risk factors etc. will be considered.

- Not related: Temporal relationship of the onset of the event, relative to administration of the product, is not reasonable or another cause can by itself explain the occurrence of the event.
- Unlikely: Temporal relationship of the onset of the event, relative to administration of the product, is likely to have another cause which can by itself explain the occurrence of the event.
- Possibly related: Temporal relationship of the onset of the event, relative to administration of the product, is reasonable but the event could have been due to another, equally likely cause.
- Probably related: Temporal relationship of the onset of the event, relative to administration of the product, is reasonable and the event is more likely explained by the product than any other cause.
- Definitely related: Temporal relationship of the onset of the event, relative to administration of the product, is reasonable and there is no other cause to explain the event, or a re-challenge (if feasible) is positive.
- Where an event is assessed as possibly related, probably related, definitely related the event is an adverse reaction.

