14.4 Expectedness

Adverse reactions must be considered as unexpected if they add significant information on the specificity or severity of an expected adverse reaction. The expectedness of an adverse reaction shall be determined according to the reference documents.

- Expected: Reaction previously identified and described in protocol and/or reference documents.
- Unexpected: Reaction not previously described in the protocol or reference documents.

All AEs occurring during the period from screening visit to the trial completion will be registered and reported if applicable.

For all adverse event/reactions the chief investigator will make an assessment of intensity, causality, expectedness and seriousness.

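### Section 14 of the protocol gives conflicting tests for which serious reactions are SUSARs: unexpectedness turns on nature and severity in one place and on either in others, and the definitely related grade is left out.

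*Protocol*

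**What the plan says.** The relevant rules are spread over section 14 of the Protocol.

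- **14.1, unexpected adverse reaction:** a reaction "the nature or severity of which is not consistent with the information about the investigational product". The reference is the product summary in section 7.
- **14.1, SSAR:** it "is any serious adverse reaction that is suspected (possibly or probably) to be related to the investigational product".
- **14.1, SUSAR:** an SSAR that is also unexpected, "meaning that its nature and severity are not consistent with the information about the investigational product". The reference here is an IB.
- **14.3:** after a five-grade causality scale, "Where an event is assessed as possibly related, probably related, definitely related the event is an adverse reaction".
- **14.4:** "Adverse reactions must be considered as unexpected if they add significant information on the specificity or severity of an expected adverse reaction".
- **Section 7, on the product:** "A sudden increase in dietary fibre may cause mild gastrointestinal disturbances, but these are generally transient".
- **14.5, SUSAR route:** the report goes to the chief investigator, the sponsor, UHS R&D and the UHS patient safety team. The sponsor informs the REC within 7 days.
- **14.5, SAE route:** the report goes within 24 hours to the chief investigator, the sponsor and UHS R&D. Related and unexpected SAEs go to the REC within 15 days of the chief investigator becoming aware.

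**The concern.** The SUSAR definition decides which serious reactions take the faster and wider reporting route. It should therefore apply the same tests of expectedness and relatedness as the rest of section 14. As written it is narrower in two ways.

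First, it joins nature and severity with *and*, where the general definition in 14.1 and the rule in 14.4 accept either. The only reaction to the product that section 7 describes is mild gastrointestinal disturbance. A worse form of that reaction is therefore the obvious case in which nature matches the product information and severity does not.

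Second, the SSAR definition lists two of the three causality grades that make an event an adverse reaction. The grade left out is the strongest.

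At stake is whether an event of either kind reaches the REC under the SUSAR limit and whether the patient safety team is told.

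**Working it through.** The plan gives no figure to reproduce, so the check compares the definitions.

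**Side by side**

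| Element | SSAR/SUSAR definitions (14.1) | Elsewhere in section 14 |
|---|---|---|
| Unexpectedness | nature and severity both inconsistent | nature or severity (14.1, unexpected adverse reaction); specificity or severity (14.4) |
| Causality grades | possibly, probably | possibly, probably, definitely (14.3) |

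**Case A: serious gastrointestinal reaction, possibly or probably related, worse than mild.** Section 14.2 separates intensity from seriousness, so the case needs both: a seriousness criterion such as hospitalisation, and an intensity above mild. Taking section 7 as the product information, nature is consistent and severity is not. Under the general definition in 14.1 and under 14.4 the reaction is unexpected. Under the literal SUSAR wording, one of the two required mismatches is absent, so it is not a SUSAR.

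**Case B: serious reaction, unexpected in both nature and severity, graded definitely related.** Under 14.3 it is an adverse reaction. By the letter it is neither possibly nor probably related, so it is not an SSAR and cannot be a SUSAR.

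**Count of definition cells.** Cross the three related grades with nature consistent (yes/no) and severity consistent (yes/no): 3 × 2 × 2 = 12 kinds of serious adverse reaction.

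- Unexpected when either mismatch is enough and all three grades count: 3 grades × 3 mismatch patterns = 9.
- SUSAR by the literal wording: 2 grades × 1 pattern (both mismatched) = 2.
- Unexpected elsewhere in section 14 but outside the SUSAR definition: 9 − 2 = 7.
- Of these 7, the conjunction alone removes 9 − (3 × 1) = 6, the missing grade alone removes 9 − (2 × 3) = 3, and 2 are removed by both: 6 + 3 − 2 = 7.

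These count combinations in the definitions. They are not probabilities of events.

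**Routing of an affected event under 14.5**

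| Step | As SUSAR | As SAE only |
|---|---|---|
| Sponsor and UHS R&D | yes | yes, within 24 hours |
| UHS patient safety team | yes | not listed |
| REC | within 7 days, start point not stated | within 15 days of the chief investigator becoming aware, if related and unexpected |
| Missing information supplied | five working days after initial report | five working days after initial report |

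**The case against.** The strongest reply is that the literal reading is not forced. The SUSAR sentence uses the term unexpected, which 14.1 has just defined with *or*. Section 14.4 is mandatory in tone and has the chief investigator judge expectedness for every event. The parenthesis in the SSAR definition can be read as a gloss on the word suspected, in a sentence that opens with any serious adverse reaction. Section 14.1 also sets the threshold for a reaction at a reasonable possibility, which a definite reaction plainly passes. A careful reader could classify both cases correctly.

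This stands as a limit on the consequence. It does not remove the contradiction, because the SUSAR sentence goes on to state what unexpected means and so supplies a second test.

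A reader might infer more than the documents support:

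- **That misrouting is certain.** It follows only from the literal wording. The general definition in 14.1 and section 14.4 give grounds to classify correctly.
- **That REC notice comes 8 days late (15 − 7).** Both limits are maxima, and 14.5 gives no start point for the 7 days, so the subtraction is not a delay. The coexistence of the two limits is also a separate conflict, since the 15-day rule for related and unexpected SAEs describes SUSARs as well. If the limits were aligned, the timing consequence would go. The patient safety team gap and the conflicting definitions would remain.
- **That SUSAR counts in the final report would be too low.** Section 14.5 plans an analysis of all AEs and SAEs and mentions no SUSAR count. An affected event is still counted as an SAE.
- **That the events go unreported.** The SAE route still takes them to the sponsor and UHS R&D within 24 hours.

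**Conclusion.** The inconsistency is real on both counts and should be corrected. Its effect is a risk that a serious reaction worse in degree than the product information describes, or one judged definitely related and unexpected, is handled as an SAE only. Such an event could miss the 7-day REC limit and the notice to the UHS patient safety team.

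The size is small. The trial has 72 participants, section 7 describes the product as well tolerated even at high intakes, and few qualifying events are likely. Neither the primary outcome nor any other analysis is affected.

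The conclusion rests on two assumptions. Section 7 is taken as the product information against which expectedness is judged; the SUSAR sentence names an IB that the protocol does not otherwise describe, which is a separate matter. The word unexpected in the 15-day SAE rule is taken in the wider sense of the general definition in 14.1 and of 14.4, so that affected events do reach the REC.

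**What to change.** Reconcile the SSAR and SUSAR definitions in 14.1 with the general definition of an unexpected adverse reaction in 14.1 and with 14.3 and 14.4:

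1. In the SUSAR definition, replace *and* with *or* between nature and severity.
2. In the SSAR definition, extend the parenthesis to possibly, probably or definitely.

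The cost is two wording changes. They add no procedure, visit or analysis; at most an occasional event moves to the SUSAR route.
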